6.6.2.1.16. Electrolyte Disorders

Serum electrolyte disorders including hyponatremia, hypokalemia, hypomagnesemia, and hypophosphatemia have been reported during treatment with cabozantinib, and serum electrolyte levels should be monitored frequently while receiving cabozantinib. Clinically relevant electrolyte disorders should be managed according to the dose modification guidelines as outlined in [Table 8](#) or as clinically indicated. Standard clinical practice guidelines should be used for management of electrolyte disorders and may include oral or IV replacement.

6.6.2.1.17. Endocrine Disorders

Treatment-emergent elevation of thyroid-stimulating hormone (TSH) has been observed with cabozantinib treatment. Currently available data are insufficient to determine the mechanism of thyroid function test alterations and its clinical relevance. Management of thyroid dysfunction (eg, symptomatic hypothyroidism) should follow accepted clinical practice guidelines.

6.6.2.2. Atezolizumab

The most common AEs reported in $\geq 20\%$ of subjects treated with atezolizumab include fatigue, decreased appetite, nausea, urinary tract infection, pyrexia, and constipation (Tecentriq USPI).

Subjects treated with atezolizumab may also develop IRRs or CRS as well as irAEs such as myocarditis, pericardial disorders, pneumonitis, hepatitis, colitis, nephritis, endocrinopathies (hypophysitis, thyroid disorders, adrenal insufficiency, Type 1 diabetes), skin disorders, severe cutaneous adverse reactions, ocular events, neurological toxicity (myasthenic syndrome/myasthenia gravis, Guillain-Barré syndrome, meningoencephalitis, facial paresis, or myelitis), pancreatitis, myositis, and embryo-fetal toxicity. Management guidance for atezolizumab-associated AEs is provided in [Sections 6.6.2.2.1](#) through [6.6.2.2.15](#).

For details on warnings & precautions, possible AEs and management guidance of AEs, and use in special patient populations refer to the local prescribing information of atezolizumab and the atezolizumab Investigator's Brochure. In addition, Investigators may be informed separately of any new urgent safety concerns that may arise through direct communication from the Sponsor (eg, Dear Investigator Letters).

The following are general recommendations for management of any other adverse events that may occur and are not specifically listed in the following subsections.

- Subjects and family caregivers should receive timely and up-to-date information about immunotherapies, their mechanism of action, and the clinical profile of possible immune-related adverse events prior to initiating therapy and throughout treatment and survival follow-up. There should be a high level of suspicion that new symptoms are treatment related.
- In general, atezolizumab therapy should be continued with close monitoring for Grade 1 toxicities, with the exception of some neurologic toxicities.
- Consider holding atezolizumab for most Grade 2 toxicities and resume when symptoms and/or laboratory values resolve to Grade 1 or better. Corticosteroids (initial dose of 0.5-1 mg/kg/day of prednisone or equivalent) may be administered.
- For Grade 2 recurrent or persistent (lasting for more than 5 days) events, treat as a Grade 3 event.
- Hold atezolizumab for Grade 3 toxicities and initiate treatment with high-dose corticosteroids (1-2 mg/kg/day prednisone or equivalent). Corticosteroids should be tapered over 1 month to 10 mg/day oral prednisone or equivalent, before atezolizumab can be resumed. If symptoms do not improve within 48 to 72 hours of high-dose corticosteroid use, other immunosuppressants may be offered for some toxicities.
- In general, Grade 4 toxicities warrant permanent discontinuation of atezolizumab treatment, with the exception of endocrinopathies that are controlled by hormone replacement therapy.

- The investigator should consider the benefit-risk balance for a given subject prior to further administration of atezolizumab. Resumption of atezolizumab may be considered in subjects who are deriving benefit and have fully recovered from the immune-related event. The decision to re-challenge subjects with atezolizumab should be based on the investigator's assessment of the benefits and risks and documented by the investigator. The Medical Monitor is available to advise as needed.

6.6.2.2.1. Infusion-Related Reactions and Cytokine Release Syndrome

IRRs are known to occur with the administration of monoclonal antibodies and have been reported with atezolizumab. These reactions, which are thought to be due to release of cytokines and/or other chemical mediators, occur within 24 hours of atezolizumab administration and are generally mild to moderate in severity.

CRS is defined as a supraphysiologic response following administration of any immune therapy that results in activation or engagement of endogenous or infused T cells and/or other immune effector cells. Symptoms can be progressive, always include fever at the onset, and may include hypotension, capillary leak (hypoxia), and end-organ dysfunction (Lee et al 2019). CRS has been well documented with chimeric antigen receptor T-cell therapies and bispecific T-cell engager antibody therapies but has also been reported with immunotherapies that target PD-1 or PD-L1 (Rotz et al 2017; Adashek and Feldman 2019), including atezolizumab.

No premedication is indicated for the first administration of atezolizumab. However, subjects who experience an IRR or CRS with atezolizumab may receive premedication with antihistamines, antipyretics, and/or analgesics (eg, acetaminophen) for subsequent infusions. Metamizole (dipyrone) is prohibited in treating atezolizumab-associated IRRs because of its potential for causing agranulocytosis.

There may be significant overlap in signs and symptoms of IRRs and CRS, and in recognition of the challenges in clinically distinguishing between the two, consolidated guidelines for medical management of IRRs and CRS are provided in [Appendix G](#).

Severe COVID-19 appears to be associated with a CRS involving the inflammatory cytokines IL-6, IL-10, IL-2, and IFN- γ (Merad and Martin 2020). If a patient develops suspected CRS during the study, a differential diagnosis should include COVID-19, which should be confirmed or refuted through assessment of exposure history, appropriate laboratory testing, and clinical or radiologic evaluations per investigator judgment. If a diagnosis of COVID-19 is confirmed, the disease should be managed as per local or institutional guidelines.

For subjects who develop COVID-19 while on study, the Investigator is to evaluate the overall risk-benefit ratio for the subject to determine whether holding study treatment(s) is in the best interest of the subject.

6.6.2.2.2. Immune-Related Pulmonary Events

Pulmonary events may present as new or worsening cough, chest pain, fever, dyspnea, fatigue, hypoxia, pneumonitis, and pulmonary infiltrates. Subjects should be assessed for pulmonary signs and symptoms throughout the study and will also have CT scans of the chest performed at every tumor assessment.

All pulmonary events should be thoroughly evaluated for other commonly reported etiologies, such as pneumonia or other infections, lymphangitic carcinomatosis, pulmonary embolism, heart failure, chronic obstructive pulmonary disease, or pulmonary hypertension. COVID-19 evaluation should be performed per institutional guidelines where relevant. Management guidelines for pulmonary events are provided in [Table 15](#).

Table 15: Management Guidelines for Immune-Related Pulmonary Events, Including Pneumonitis

Severity of Event	Management
Grade 1	
 Continue atezolizumab and monitor closely. Re-evaluate on serial imaging. Consider subject referral to pulmonary specialist. For Grade 1 pneumonitis, consider withholding atezolizumab.
Grade 2	
 Withhold atezolizumab for up to 12 weeks after event onset.^a Refer subject to pulmonary and infectious disease specialists and consider bronchoscopy or BAL with or without transbronchial biopsy. Initiate treatment with 1–2 mg/kg/day oral prednisone or equivalent. Resume atezolizumab if event resolves to Grade 1 or better.^b Permanently discontinue atezolizumab and contact the Sponsor if event does not resolve to Grade 1 or better while withholding atezolizumab.^{c,d} For recurrent events or events with no improvement after 48–72 hours of corticosteroids, treat as a Grade 3 or 4 event
Grade 3 or 4	
 Permanently discontinue atezolizumab and contact the Sponsor.^c Oral or IV broad-spectrum antibiotics should be administered in parallel to the immunosuppressive treatment. Bronchoscopy or BAL with or without transbronchial biopsy is recommended. Initiate treatment with 1–2 mg/kg/day IV methylprednisolone or equivalent. If event does not improve within 48 hours after initiating corticosteroids, consider adding an immunosuppressive agent. If event resolves to Grade 1 or better, taper corticosteroids over ≥ 1 month.

BAL, bronchoscopic alveolar lavage.

^a Atezolizumab may be withheld for a period of time beyond 12 weeks to allow for corticosteroids to be reduced to ≤ 10 mg/day oral prednisone or equivalent. The acceptable length of the extended period of time must be based on the investigator's benefit–risk assessment and in alignment with the protocol requirements for duration of treatment and documented by the Investigator a. The Medical Monitor is available to advise as needed.

^b If corticosteroids have been initiated, they must be tapered over ≥ 1 month to ≤ 10 mg/day oral prednisone or equivalent before atezolizumab can be resumed.

^c Resumption of atezolizumab may be considered in subjects who are deriving benefit and have fully recovered from the immune-related event. The decision to rechallenge subjects with atezolizumab should be based on the investigator's benefit–risk assessment and documented by the investigator. The Medical Monitor is available to advise as needed.

^d In case of pneumonitis, atezolizumab should not be resumed after permanent discontinuation.

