6.6.2.2.10. Immune-Related Nephritis

Immune-related nephritis has been associated with the administration of atezolizumab. Eligible patients must have adequate renal function. Renal function, including serum creatinine, should be monitored throughout study treatment. Patients with abnormal renal function should be evaluated and treated for other more common etiologies (including prerenal and postrenal causes, and concomitant medications such as non-steroidal anti-inflammatory drugs). Refer the patient to a renal specialist if clinically indicated. A renal biopsy may be required to enable a definitive diagnosis and appropriate treatment.

Atezolizumab should be withheld for moderate (Grade 2) immune-related nephritis and permanently discontinued for severe nephritis (Grade 3 or 4). Refer subjects to a renal specialist and consider renal biopsy and supportive measures as indicated. Corticosteroids and/or additional immunosuppressive agents should be administered as clinically indicated. Refer to the current atezolizumab Investigator's Brochure for further guidance on the management of immune-related nephritis.

Subjects with signs and symptoms of nephritis, in the absence of an identified alternate etiology, should be treated according to the guidelines in [Table 24](#).

Table 24: Management Guidelines for Immune-Related Nephritis

Event	Management
Renal event, Grade 1	
 Continue atezolizumab. Monitor kidney function closely, including creatinine and urine protein, until values resolve to within normal limits or to baseline values.
Renal event, Grade 2	
 Withhold atezolizumab for up to 12 weeks after event onset.^a Refer patient to renal specialist. Initiate treatment with corticosteroids equivalent to 1–2 mg/kg/day oral prednisone. If event resolves to Grade 1 or better, resume atezolizumab.^b If event does not resolve to Grade 1 or better while withholding atezolizumab, permanently discontinue atezolizumab and contact Medical Monitor.^c

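### Table 15 (Protocol 6.6.2.2.2) attaches the ban on resuming atezolizumab after pneumonitis to the unresolved Grade 2 bullet but not to the Grade 3 or 4 bullet: a minor inconsistency in operative safety text

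*Protocol*

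**What the plan says.** Table 15 in Protocol Section 6.6.2.2.2 is titled "Management Guidelines for Immune-Related Pulmonary Events, Including Pneumonitis", so it covers pulmonary events other than pneumonitis as well. Its Grade 1 row gives pneumonitis its own instruction: "For Grade 1 pneumonitis, consider withholding atezolizumab".

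The table requires permanent discontinuation in two places:

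- **Grade 2 row.** Atezolizumab is stopped for good "if event does not resolve to Grade 1 or better while withholding atezolizumab.^{c,d" (the superscript is c,d). The same row adds: "For recurrent events or events with no improvement after 48–72 hours of corticosteroids, treat as a Grade 3 or 4 event".
- **Grade 3 or 4 row.** The bullet, run together with the one after it, reads "Permanently discontinue atezolizumab and contact the Sponsor.^c Oral or IV broad-spectrum antibiotics should be administered in parallel". The only marker is c.

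Footnote c is permissive: "Resumption of atezolizumab may be considered in subjects who are deriving benefit and have fully recovered from the immune-related event". It leaves the decision to the investigator on a documented benefit-risk assessment, with the Medical Monitor available for advice. Footnote d, printed directly below it, is the prohibition: "In case of pneumonitis, atezolizumab should not be resumed after permanent discontinuation".

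Table 10 in Section 6.6.1 also lists Grade 3 or 4 pneumonitis among the events that require permanent discontinuation. Its footnote b gives a general permission to consider resumption with no pneumonitis exception, but no marker for footnote b is visible in the table.

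**The concern.** A footnote letter tells a site which qualification governs a given instruction. Followed by its letters alone, Table 15 bars resumption after Grade 2 pneumonitis that failed to resolve, and points only to the permissive footnote after Grade 3 or 4 pneumonitis. That order is clinically inverted.

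This is dosing guidance that sites act on. What is at stake is that an investigator who looks up the footnote attached to the Grade 3 or 4 bullet, and stops there, could consider giving atezolizumab again after severe pneumonitis, which footnote d forbids.

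**Working it through.** No calculation applies. The check is to trace each marker in Table 15 to its footnote and then look for the same rule elsewhere.

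**Step 1: markers in Table 15.**

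| Footnote | Content | Where it is attached |
|---|---|---|
| a | withholding may run beyond 12 weeks | Grade 2, withhold bullet |
| b | steroid taper before resuming | Grade 2, resume bullet |
| c | resumption may be considered | Grade 2 unresolved bullet; Grade 3 or 4 bullet |
| d | no resumption for pneumonitis | Grade 2 unresolved bullet only |

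Of the two permanent-discontinuation bullets, one carries d and one does not.

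**Step 2: routes for a patient with pneumonitis.**

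- Grade 2, not resolved while the drug is withheld: c and d.
- Grade 2, recurrent: handled under the Grade 3 or 4 row, so c.
- Grade 2, no improvement after 48 to 72 hours of corticosteroids: Grade 3 or 4 row, so c.
- Grade 3 or 4: c.

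By markers, only the first route leads to the ban.

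**Step 3: the words of footnote d.** It sets two conditions: the event is pneumonitis, and atezolizumab has been permanently discontinued. It sets no grade. A patient who reaches permanent discontinuation by any of the four routes meets both conditions. By wording, all four lead to the ban.

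**Step 4: is footnote c wrong on the Grade 3 or 4 row?** No. The table covers all immune-related pulmonary events, and c can properly apply to those that are not pneumonitis. What the row lacks is d alongside c.

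**Step 5: the rule elsewhere.** Table 10 requires permanent discontinuation for Grade 3 or 4 pneumonitis but says nothing about later resumption in that condition. Its footnote b is permissive, with unknown scope because no marker is visible. The resumption bullet in the general part of Section 6.6.2.2 is also permissive, but the introduction to those bullets confines them to events not listed in the subsections that follow. Pneumonitis is listed in 6.6.2.2.2, so that bullet does not compete with footnote d. Footnote d is therefore the only statement of the ban in the two documents, and its marker appears once.

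**The case against.** The strongest reply is that the rule is present and complete. Footnote d names the condition, names no grade, and sits directly under footnote c. A site would have to read c and pass over the next line to go wrong. This stands, and it is why the point is an inconsistency between markers and wording.

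A second reply is that markers in these tables are loose in general. In Table 17, the Grade 2-3 hypophysitis withhold bullet carries the steroid-taper footnote where the extended-withholding footnote would fit, and a Grade 4 steroid bullet carries the extended-withholding one. In Table 25, the footnote letter sits on the abbreviation line instead of the resumption text. This also stands in part. A careful reader should not let a letter override explicit words, and some of these slips may come from PDF extraction. The c,d pair did survive in the row directly above, which makes a lost d less likely but does not exclude it.

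A reader might go further and infer that the missing letter is deliberate, pointing to the nephritis table (Table 24), where the unresolved Grade 2 bullet carries the resumption footnote ("permanently discontinue atezolizumab and contact Medical Monitor.^c") and the Grade 3 or 4 bullet does not. The documents do not support that inference. Given the looseness just described, and because the most severe rows of several other tables do carry the resumption footnote, Table 24 says little about the intent for pneumonitis.

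Other safeguards exist. Both bullets call for contact with the Sponsor at discontinuation, footnote c requires full recovery and a documented assessment, and Section 6.6.2.2 sends sites to prescribing information that is not among the documents. These reduce the risk. They do not remove it, because nothing in the two documents makes resumption subject to Sponsor approval.

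**Conclusion.** The markers and the wording of Table 15 disagree, and the fault lies in operative safety text. Footnote d, read as written, forbids resumption after permanent discontinuation for pneumonitis of any grade. Its marker is attached to the unresolved Grade 2 bullet only, and no other sentence in the protocol or SAP restates the ban. An omitted letter is a plausible explanation, but the documents cannot prove it.

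The size is minor: one missing letter on one of two bullets. A reader might infer that the protocol permits resumption after severe pneumonitis, or that the sponsor chose this. Neither follows, since footnote d's own words reach the Grade 3 or 4 row. A reader might also try to project a patient count from the pneumonitis cases in the cited Phase 1b study of atezolizumab with bevacizumab (Section 1.3). That was a different combination, and the cases are not resumptions, so no count is offered. No endpoint, sample size, error rate or analysis is affected.

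The conclusion assumes that the extracted text shows the superscripts as printed. If the source PDF already has d on the Grade 3 or 4 bullet, the inconsistency disappears.

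**What to change.** 1. Check the marker on the Grade 3 or 4 bullet of Table 15 in the source PDF.
2. If d is absent, change that marker from c to c,d. Keep c, because it applies to non-pneumonitis events.
3. Add *except pneumonitis (see d)* to Table 15 footnote c.
4. Establish where Table 10 footnote b is anchored. If it covers Grade 3 or 4 pneumonitis, add the same exception there.
5. Tell sites, in a routine clarification, that atezolizumab is not to be resumed after permanent discontinuation for pneumonitis of any grade.

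The cost is one footnote letter, one short addition to a footnote (two if Table 10 footnote b applies) and one line to sites. No new data, visits or analyses are needed.

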6.6.2.2.3. Immune-Related Colitis or Diarrhea

Immune-related colitis has been associated with the administration of atezolizumab.

Management guidelines for diarrhea or colitis are provided in [Table 16](#).

All events of diarrhea or colitis should be thoroughly evaluated for other more common etiologies. For events of significant duration or magnitude or associated with signs of systemic

inflammation or acute-phase reactants (eg, increased c-reactive protein, platelet count, or bandemia): perform sigmoidoscopy (or colonoscopy, if appropriate) with colonic biopsy, with three to five specimens for standard paraffin block to check for inflammation and lymphocytic infiltrates to confirm colitis diagnosis.

Table 16: Management Guidelines for Immune-Related Diarrhea or Colitis

Severity of Event	Management
Grade 1	
 Continue atezolizumab Initiate symptomatic treatment Endoscopy is recommended if symptoms persist for > 7 days Monitor closely
Grade 2	
 Withhold atezolizumab for up to 12 weeks after event onset ^a Initiate symptomatic treatment If strong clinical suspicion for immune-related colitis, start empiric IV steroids while waiting for definitive diagnosis Subject referral to GI specialist is recommended For recurrent events or events that persist > 5 days, initiate treatment with 1–2 mg/kg/day oral prednisone or equivalent. If the event does not improve within 48 hours after initiating corticosteroids, consider adding an immunosuppressive agent. Resume atezolizumab if event resolves to Grade 1 or better ^{a,b} Permanently discontinue atezolizumab and contact the Sponsor if event does not resolve to Grade 1 or better while withholding atezolizumab ^c
Grade 3	
 Withhold atezolizumab for up to 12 weeks after event onset ^a Refer subject to GI specialist for evaluation and confirmatory biopsy Initiate treatment with 1–2 mg/kg/day IV methylprednisolone or equivalent and convert to 1–2 mg/kg/day oral prednisone or equivalent upon improvement. If event does not improve within 48 hours after initiating corticosteroids, consider adding an immunosuppressive agent. Resume atezolizumab if event resolves to Grade 1 or better ^b Permanently discontinue atezolizumab and contact the Sponsor if event does not resolve to Grade 1 or better while withholding atezolizumab ^c
Grade 4	
 Permanently discontinue atezolizumab and contact the Sponsor. ^c Refer subject to GI specialist for evaluation and confirmatory biopsy. Initiate treatment with 1–2 mg/kg/day IV methylprednisolone or equivalent and convert to 1–2 mg/kg/day oral prednisone or equivalent upon improvement. If event does not improve within 48 hours after initiating corticosteroids, consider adding an immunosuppressive agent. If event resolves to Grade 1 or better, taper corticosteroids over ≥ 1 month.

GI, gastrointestinal; IV, intravenous

- ^a Atezolizumab may be withheld for a period of time beyond 12 weeks to allow for corticosteroids to be reduced to ≤ 10 mg/day oral prednisone or equivalent. The acceptable length of the extended period of time must be based on the assessment of benefit-risk by the investigator and in alignment with the protocol requirements for duration of treatment and documented by the investigator. The Medical Monitor is available to advise as needed.
- ^b If corticosteroids have been initiated, they must be tapered over ≥ 1 month to ≤ 10 mg/day oral prednisone or equivalent before atezolizumab can be resumed.
- ^c Resumption of atezolizumab may be considered in subjects who are deriving benefit and have fully recovered from the immune-related event. The decision to rechallenge with atezolizumab should be based on investigator's assessment of benefit-risk, and documented by the investigator. The Medical Monitor is available to advise as needed.

